**5.6.18. Study procedures during special circumstances****(Amended 26 May 2020)**

*During special circumstances (e.g., COVID-19 pandemic), the specific guidance from local public health and other competent authorities regarding the protection of individuals' welfare must be applied. For the duration of such special circumstances, the following measures may be implemented for enrolled participants (still participating in the study) for Visit 10:*

- *If despite best efforts it is not possible to collect the biological samples within the interval predefined in the protocol (see Table 6), then the interval may be extended up to a maximum length of 120 days (i.e. allowed interval for Visit 10 = 360 to 390 days +120 days under special circumstances).*
- *In case, a physical visit to the clinic is not possible in any circumstances even with the extended interval, safety follow-up may be made by a telephone call or other means of virtual contact, if appropriate. The telephone call/ mode of virtual contact will be considered equivalent to study conclusion visit.*

**CONFIDENTIAL**207759 (NTHI MCAT-008)  
Protocol Amendment 3 Final**5.6.19. Study conclusion**

The investigator will:

- Review data collected to ensure accuracy and completeness
- Complete the Study Conclusion screen in the eCRF.

**5.7. Biological sample handling and analysis**

Please refer to the SPM and Central Laboratory manual for details on biospecimen management (handling, storage and shipment).

Samples will not be labelled with information that directly identifies the subject but will be coded with the identification number for the subject (subject number).

- Collected samples will be used for protocol mandated research and purposes related to the improvement, development and quality assurance of the laboratory tests described in this protocol. This may include the management of the quality of these tests, the maintenance or improvement of these tests, the development of new test methods, as well as making sure that new tests are comparable to previous methods and work reliably.
- It is also possible that future findings may make it desirable to use the samples acquired in this study for future research, not described in this protocol. Therefore, all subjects in countries where this is allowed will be asked to give a specific consent to allow GSK or a contracted partner to use the samples for future research. Future research will be subject to the laws and regulations in the respective countries and will only be performed once an independent Ethics Committee or Review Board has approved this research.

Information on further investigations and their rationale can be obtained from GSK Biologicals.

Any sample testing will be done in line with the consent of the individual subject.

Refer also to the [Investigator Agreement](#), where it is noted that the investigator cannot perform any other biological assays except those described in the protocol or its amendment(s).

Collected samples will be stored for a maximum of 20 years (counting from when the last subject performed the last study visit), unless local rules, regulations or guidelines require different timeframes or different procedures, which will then be in line with the subject consent. These extra requirements need to be communicated formally to and discussed and agreed with GSK Biologicals.

**CONFIDENTIAL**207759 (NTHI MCAT-008)  
Protocol Amendment 3 Final**5.7.1. Use of specified study materials**

When materials are provided by GSK Biologicals and/or a central laboratory, it is MANDATORY that all clinical samples (including serum samples) be collected and stored exclusively using those materials in the appropriate manner. The use of other materials could result in the exclusion of the subject from the per-protocol analysis (See Section 10.5 for the definition of cohorts to be analysed). The investigator must ensure that his/her personnel and the laboratory(ies) under his/her supervision comply with this requirement. However, when GSK Biologicals and/or a central laboratory does not provide material for collecting and storing clinical samples, appropriate materials from the investigator's site must be used. Refer to the Module on Clinical Trial Supplies in the SPM and to the Central Laboratory investigator manual.

**5.7.2. Biological samples**

(Amended 26 May 2020)

**Table 7 Biological samples**

| Sample type                      | Quantity | Unit | Timepoint  | Sub-cohort            |
|----------------------------------|----------|------|--|-----------------------|
| Blood for humoral immunogenicity | ~20      | ml   | 
 
• Visit 1 (Day 1)
 
• Visit 4 (Day 91)
 
• Visit 5 (Day 181)
 
• Visit 6 (Day 211)
 
• Visit 7 (Day 361)
 
• Visit 8 (Day 391)
 
• Visit 9 (Day 541)
 
• Visit 10 (Day 721)**
 
 | All enrolled subjects |
| Blood for CMI                    | ~40      | ml   | 
 
• Visit 1 (Day 1)
 
• Visit 4 (Day 91)
 
• Visit 5 (Day 181)
 
• Visit 6 (Day 211)
 
• Visit 7 (Day 361)
 
• Visit 8 (Day 391)
 
  | Sub-cohort for CMI*   |

\*Refer to Section 4.1 for sub-cohort description.

\*\* Refer to Section 5.6.18 for study procedures to be considered during special circumstances and Table 6 for details on extended visit interval.

**5.7.3. Laboratory assays**

Please refer to APPENDIX A for a detailed description of the assays performed in the study. Please refer to APPENDIX B for the address of the clinical laboratories used for sample analysis.

**Humoral antibody responses**

Total IgG concentrations will be measured by ELISA at GSK Biologicals' laboratory or a GSK designated laboratory using qualified procedures.

**CONFIDENTIAL**207759 (NTHI MCAT-008)  
Protocol Amendment 3 Final**Table 8 Humoral Immunity (Antibody determination)**

| System | Component           | Method | Kit / Manufacturer | Unit* | Cut-off* | Laboratory   |
|--------|---------------------|--------|--------------------|-------|----------|--|
| SERUM  | anti-PilA antibody  | ELISA  | In house           | EU/mL | 8        | GSK
Biologicals**
or GSK
designated
laboratory |
|        | anti-PE antibody    |        |                    |       | 16       |  |
|        | anti-PD antibody    |        |                    |       | 153      |  |
|        | anti-UspA2 antibody |        |                    |       | 28       |  |

EU/mL = ELISA unit per millilitre

\*Assay cut-off and unit might be subject to change during the course of the study (e.g. in case of assay re-optimization, qualification, (re)validation or standardization). In this case, this will be documented in the clinical study report.

\*\*GSK Biologicals laboratory refers to the Clinical Laboratory Sciences (CLS) in Rixensart, Belgium; Wavre, Belgium; Marburg, Germany.

Other assays may be developed and/or validated on blood samples with the aim to measure the immune response to any component of either the NTHi-Mcat investigational vaccines and/or to other respiratory pathogens. The research may include but is not limited to functional assays such as serum bactericidal activity assays against NTHi and/or Mcat.

**Cell-mediated immune responses**

CMI assays will be performed at GSK Biologicals or GSK designated laboratory using qualified procedures.

**Table 9 Cell-mediated Immunity (CMI) using flow cytometry**

| System | Component Family                                    | Scale        | Method             | Unit   | Laboratory                                       |
|--------|---|--------------|--------------------|--|--|
| PBMCs  | Specific CD4 + /CD8 + T-cells | Quantitative | Flow cytometry ICS | Number of specific CD4 + /CD8 + T-cells /10  | GSK Biologicals*
or GSK designated laboratory |

PBMC = peripheral blood mononuclear cell; ICS = intracellular cytokine staining

\*GSK Biologicals laboratory refers to the Clinical Laboratory Sciences (CLS) in Rixensart, Belgium; Wavre, Belgium; Marburg, Germany.

Additional testing on peripheral blood mononuclear cells (PBMCs), such as, but not limited to, evaluation of NTHi and/or Mcat-specific memory B-cells, intracellular cytokine staining (ICS) testing using other bacterial antigens, may be done during the study or after study completion, should these data be required for accurate interpretation of the data and/ or for further research related to the investigational vaccine and/ or the disease, should such test(s) become available at GSK Biologicals' laboratory or a laboratory designated by GSK Biologicals.

Additional exploratory testing related to the vaccine and/or the disease under study may be performed on the samples within the framework of the study if deemed necessary for accurate interpretation of the data or should such assay(s) become available at GSK. These assays may not be represented in the objectives/endpoints of the study protocol.

The GSK Biologicals' clinical laboratories have established a Quality System supported by procedures. The activities of GSK Biologicals' clinical laboratories are audited regularly for quality assessment by an internal (sponsor-dependent) but laboratory-independent Quality Department.

**CONFIDENTIAL**207759 (NTHI MCAT-008)  
Protocol Amendment 3 Final**5.7.4. Biological samples evaluation****5.7.4.1. Immunological read-outs**

(Amended 26 May 2020)

**Table 10 Immunological read-outs**

| Blood sampling timepoint      |                    | Sub-cohort Name | No. subjects | Component                                  |
|-------------------------------|--------------------|-----------------|--------------|--|
| Type of contact and timepoint | Sampling timepoint |                 |              |  |
| Visit 1 (Day 1)               | Pre-Vacc I         | All subjects    | ~200         | Anti-PD, Anti-PE, Anti-PilA and Anti-UspA2 |
|                               |                    | CMI sub-cohort* | ~40          | Specific CD4+/CD8+ T-cells                 |
| Visit 4 (Day 91)              | Post-Vacc II       | All subjects    | ~200         | Anti-PD, Anti-PE, Anti-PilA and Anti-UspA2 |
|                               |                    | CMI sub-cohort* | ~40          | Specific CD4+/CD8+ T-cells                 |
| Visit 5 (Day 181)             | Pre-Vacc III       | All subjects    | ~200         | Anti-PD, Anti-PE, Anti-PilA and Anti-UspA2 |
|                               |                    | CMI sub-cohort* | ~40          | Specific CD4+/CD8+ T-cells                 |
| Visit 6 (Day 211)             | Post-Vacc III      | All subjects    | ~200         | Anti-PD, Anti-PE, Anti-PilA and Anti-UspA2 |
|                               |                    | CMI sub-cohort* | ~40          | Specific CD4+/CD8+ T-cells                 |
| Visit 7 (Day 361)             | Pre-Vacc IV        | All subjects    | ~200         | Anti-PD, Anti-PE, Anti-PilA and Anti-UspA2 |
|                               |                    | CMI sub-cohort* | ~40          | Specific CD4+/CD8+ T-cells                 |
| Visit 8 (Day 391)             | Post-Vacc IV       | All subjects    | ~200         | Anti-PD, Anti-PE, Anti-PilA and Anti-UspA2 |
|                               |                    | CMI sub-cohort* | ~40          | Specific CD4+/CD8+ T-cells                 |
| Visit 9 (Day 541)      | Post-Vacc IV       | All subjects    | ~200         | Anti-PD, Anti-PE, Anti-PilA and Anti-UspA2 |
| Visit 10 (Day 721)**   | Post-Vacc IV       | All subjects    | ~200         | Anti-PD, Anti-PE, Anti-PilA and Anti-UspA2 |

\*Approximately 20% of the subjects in each group will be part of a sub-cohort for CMI analysis.

**\*\* Refer to Section 5.6.18 for study procedures to be considered during special circumstances and Table 6 for details on extended visit interval.****5.7.5. Immunological correlates of protection**

No generally accepted immunological correlate of protection has been demonstrated so far for the antigens used in the candidate vaccine.

**CONFIDENTIAL**207759 (NTHI MCAT-008)  
Protocol Amendment 3 Final**6. STUDY VACCINES AND ADMINISTRATION****6.1. Description of study vaccines**

The candidate vaccine to be used has been developed and manufactured by GSK Biologicals.

The Quality Control Standards and Requirements for the candidate vaccine are described in separate Quality Assurance documents (e.g. release protocols, certificate of analysis) and the required approvals have been obtained.

The vaccines are labelled and packed according to applicable regulatory requirements.

**Table 11 Study vaccines**

| Treatment name | Vaccine/
product name | Formulation   | Presentation                           | Volume to
be
administered | Number of
doses |
|----------------|--------------------------|---|--|---------------------------------|--------------------|
| 10-10-3/AS01E  | NTHi-Mcat 10-10-3        | PD=10µg; PE-PilA=10µg;
UspA2=3.3µg   | Freeze-dried antigens in monodose vial | 0.5 ml                          | 3                  |
|                | AS01E                    | MPL=25µg; QS21=25µg;
Liposomes   | Liquid in monodose vial                |                                 |                    |
| Placebo        | Formulation buffer S9b   | Na 2 HPO 4 =0.4mg;
KH 2 PO 4 =56µg;
NaCl=1,16mg; KCl=30µg;
MgCl 2 =15µg | Liquid in monodose vial                | 0.5 ml                          | 1                  |

**MPL** = 3-O-desacyl-4'-monophosphoryl lipid A; **QS-21** = Quillaja saponaria Molina, fraction 21 (Licensed by GSK from Antigenics Inc, a wholly owned subsidiary of Agenus Inc., a Delaware, USA corporation).

**6.2. Storage and handling of study vaccines**

The study vaccines must be stored at the respective label storage temperature conditions in a safe and locked place. Access to the storage space should be limited to authorized study personnel. The storage conditions will be assessed during pre-study activities under the responsibility of the sponsor study contact. The storage temperature should be continuously monitored with calibrated (if not validated) temperature monitoring device(s) and recorded. Refer to the Module on Clinical Trial Supplies in the SPM for more details on storage of the study vaccines.

Temperature excursions must be reported in degree Celsius.

Any temperature excursion outside the range of 0.0 to +8.0°C (for +2 to +8°C label storage condition) impacting investigational medicinal products (IMPs) must be reported in the appropriate (electronic) temperature excursion decision form ([e]TDF). The impacted IMPs must not be used and must be stored in quarantine at label temperature conditions until usage approval has been obtained from the sponsor.

**CONFIDENTIAL**207759 (NTHI MCAT-008)  
Protocol Amendment 3 Final

In case of temperature excursion below +2.0°C down to 0.0°C impacting IMP(s) there is no need to report in (e)TDF, but adequate actions must be taken to restore the +2 to +8°C label storage temperature conditions. The impacted IMP(s) may still be administered, but the site should avoid re-occurrence of such temperature excursion. Refer to the Module on Clinical Trial Supplies in the SPM for more details on actions to take.

Refer to the Module on Clinical Trial Supplies in the SPM for details and instructions on the temperature excursion reporting and usage decision process, packaging and accountability of the study vaccines.

**6.3. Dosage and administration of study vaccines****Table 12 Dosage and administration**

| Type of contact and timepoint | Study group | Treatment name | Volume to be administered | Route  | Site     |                             |                         |
|-------------------------------|-------------|----------------|---------------------------|--------------------|----------|-----------------------------|-------------------------|
|                               |             |                |                           |                    | Location | Directionality  | Laterality  |
| Visit 1 (Day 1)               | Schedule 1  | 10-10-3/AS01E  | 0.5 ml                    | IM                 | Deltoid  | Upper                       | Non-dominant            |
|                               | Schedule 2  |                |                           |                    |          |                             |                         |
| Visit 3 (Day 61)              | Schedule 1  | 10-10-3/AS01E  | 0.5 ml                    | IM                 | Deltoid  | Upper                       | Non-dominant            |
|                               | Schedule 2  |                |                           |                    |          |                             |                         |
| Visit 5 (Day 181)             | Schedule 1  | 10-10-3/AS01E  | 0.5 ml                    | IM                 | Deltoid  | Upper                       | Non-dominant            |
|                               | Schedule 2  | Placebo        |                           |                    |          |                             |                         |
| Visit 7 (Day 361)             | Schedule 1  | Placebo        | 0.5 ml                    | IM                 | Deltoid  | Upper                       | Non-dominant            |
|                               | Schedule 2  | 10-10-3/AS01E  |                           |                    |          |                             |                         |

 Intramuscular (IM)

 Directionality is a qualifier for further detailing the location of the vaccine administration (e.g. Upper, Lower)

 The non-dominant arm is the preferred arm of injection. In case it is not possible to administer the vaccine in the non-dominant arm, an injection in the dominant arm may be performed.

The investigational NTHi-Mcat vaccine needs to be reconstituted. Please refer to the SPM for more detailed instructions on study vaccine preparation.

**6.4. Replacement of unusable vaccine doses**

In addition to the vaccine doses provided for the planned number of subjects (including over-randomisation when applicable), at least 20 % additional vaccine doses will be supplied to replace those that are unusable.

The investigator will use SBIR to obtain the replacement vial number. The replacement numbers will be allocated by dose. The system will ensure, in a blinded manner, that the replacement vial matches the formulation the subject was assigned to by randomisation.

**CONFIDENTIAL**207759 (NTHI MCAT-008)  
Protocol Amendment 3 Final**6.5. Contraindications to subsequent vaccination**

The following events constitute absolute contraindications to further administration of NTHi-Mcat vaccine. If any of these events occur during the study, the subject must not receive additional doses of vaccine but may continue other study procedures at the discretion of the investigator (see Section 8.5).

- Anaphylaxis following the administration of vaccine.
- Pregnancy (see Section 8.2.1).
- Any confirmed or suspected immunosuppressive or immunodeficient condition, based on medical history and physical examination (no laboratory testing required).
- Any condition that in the judgment of the investigator would make intramuscular injection unsafe.
- Current auto-immune disease.
- Malignancy (excluding non-melanotic skin cancer and carcinoma in situ of the cervix, if considered cured) or lymphoproliferative disorder.
- Occurrence of a new pIMD or the exacerbation of an existing pIMD that, in the opinion of the investigator, exposes the subject to unacceptable risk from subsequent vaccination. In such cases, the investigator should use his/her clinical judgement prior to administering the next dose of the vaccine. Refer to Section 8.1.5.1 for the definition of pIMDs.

The following events constitute contraindications to administration of NTHi-Mcat vaccine at that point in time; if any of these events occur at the time scheduled for vaccination, the subject may be vaccinated at a later date, within the time window specified in the protocol (see Section 5.5), or the subject may be withdrawn at the discretion of the investigator (see Section 8.5).

- Acute disease and/or fever at the time of vaccination.
  - Fever is defined as temperature  $\geq 37.5^{\circ}\text{C}$ . The preferred location for measuring temperature in this study will be the oral cavity or the axilla.
  - Subjects with a minor illness (such as mild diarrhoea, mild upper respiratory infection) without fever can be administered all vaccines at the discretion of the investigator.

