## CONFIDENTIAL

207759 (NTHI MCAT-008)  
Protocol Amendment 3 Final**8.3. Detecting and recording adverse events, serious adverse events and pregnancies****8.3.1. Time period for detecting and recording adverse events, serious adverse events and pregnancies****(Amended 26 May 2020)**

All AEs starting within 30 days following administration of each dose of study vaccine (Day 1 to Day 30) must be recorded into the appropriate section of the eCRF, irrespective of intensity or whether or not they are considered vaccination-related.

The time period for collecting and recording SAEs will begin at the first receipt of study vaccine and will end at the last study visit. See Section 8.4 for instructions on reporting of SAEs.

All AEs/SAEs leading to withdrawal from the study will be collected and recorded from the time of the first receipt of study vaccine.

***For Epoch 002, this includes the assessment of COVID-19 cases in accordance with the current WHO definition. Cases should be categorised as AEs (unsolicited or AEs leading to withdrawal) or SAEs (refer to Section 8.1 for safety definitions), and routine procedures for recording, evaluation, follow-up, and reporting of AEs, and SAEs should be followed in accordance with the time period set out in Table 16.***

In addition to the above-mentioned reporting requirements and in order to fulfil international reporting obligations, SAEs that are related to study participation (i.e. protocol-mandated procedures, invasive tests, a change from existing therapy) or are related to a concurrent GSK medication/vaccine will be collected and recorded from the time the subject consents to participate in the study until she/he is discharged from the study.

The time period for collecting and recording pregnancies will begin at the first receipt of study vaccine and will end at last study visit. See section 8.4 for instructions on reporting of pregnancies.

The time period for collecting and recording of pIMDs will begin at the first receipt of study vaccine and will end at the last study visit. See section 8.4 for instructions on reporting of pIMDs.

An overview of the protocol-required reporting periods for AEs, SAEs, and pregnancies is given in Table 16.

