**8.5.1.2. Follow-up after the subject is discharged from the study**

The investigator will follow subjects:

- With SAEs, pIMDs (serious or non-serious), or subjects withdrawn from the study as a result of an AE, until the event has resolved, subsided, stabilised, disappeared, or until the event is otherwise explained, or the subject is lost to follow-up.

If the investigator receives additional relevant information on a previously reported SAE, he/she will provide this information to GSK Biologicals using a paper/ electronic Expedited Adverse Events Report and/or pregnancy report as applicable.

GSK Biologicals may request that the investigator performs or arranges the conduct of additional clinical examinations/tests and/or evaluations to elucidate as fully as possible the nature and/or causality of the AE or SAE. The investigator is obliged to assist. If a subject dies during participation in the study or during a recognised follow-up period, GSK Biologicals will be provided with any available post-mortem findings, including histopathology.

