**9.2.2. Subject withdrawal from study vaccines**

A 'withdrawal' from the study vaccines refers to any subject who does not receive the complete treatment, i.e. when no further planned dose is administered from the date of withdrawal. A subject withdrawn from the study vaccines may not necessarily be withdrawn from the study as further study procedures or follow-up may be performed (safety or immunogenicity) if planned in the study protocol.

Information relative to premature discontinuation of the study vaccines will be documented on the Vaccine Administration screen of the eCRF. The investigator will document whether the decision to discontinue further vaccination/treatment was made by the subject himself/herself, or by the investigator, as well as which of the following possible reasons was responsible for withdrawal:

- Serious adverse event.
- Unsolicited non-serious adverse event.
- Solicited adverse event
- Not willing to be vaccinated
- Other (specify).

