**10. STATISTICAL METHODS****10.1. Primary endpoints**

- Solicited local and general symptoms.
  - Occurrence of each solicited local and general symptom (any and Grade 3) reported within 7 days (Day 1 – Day 7) after each vaccination, within each vaccination schedule.
- Unsolicited adverse events.
  - Occurrence of each unsolicited AE reported within 30 days (Day 1 – Day 30) after any vaccination, according to the Medical Dictionary for Regulatory Activities (MedDRA) classification, within each vaccination schedule.
- Serious adverse events.
  - Occurrence of any serious adverse events reported from Day 1 (Visit 1) up to and including Day 541 (Visit 9), within each vaccination schedule.
- Potential Immune-mediated diseases (pIMDs).

**CONFIDENTIAL**207759 (NTHI MCAT-008)  
Protocol Amendment 3 Final

- Occurrence of pIMDs reported from Day 1 (Visit 1) up to and including Day 541 (Visit 9), within each vaccination schedule.

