- the duration of solicited adverse events will be calculated as the sum of the consecutive days with the symptom reported at Grade 1 or higher. The duration of solicited events at a specific grade (e.g., Grade 3) will be calculated as the sum of the consecutive days with the symptom reported at that grade. The same rule applies for solicited adverse events ongoing at the end of the solicited follow-up period considering the maximum intensity reported;
- when the occurrences of solicited adverse events are summarised, each event recorded as having occurred during a specific period will be counted as the number of occurrences the event is consecutively reported (at Grade 1 or higher);
- when the occurrences of solicited adverse events at a specific grade are summarised, each event recorded as having occurred at that grade during a specific period will be counted as the number of occurrences the event is consecutively reported at that grade.

For analysis of unsolicited adverse events, such as serious adverse events or adverse events by primary MedDRA term, and for the analysis of concomitant medications, all vaccinated subjects will be considered. Subjects who did not report the event or the concomitant medication will be considered as subjects without the event or the concomitant medication respectively. Note that for all tables described in this section, the way the percentage of subjects will be derived will depend on the event analysed (see table below for details). As a result, the N value will differ from one table to another.

**CONFIDENTIAL**207759 (NTHI MCAT-008)  
Statistical Analysis Plan Amendment 1 Final

Event	N used for deriving % per subject for Vaccination phase	N used for deriving % per dose for Vaccination phase
Concomitant vaccination	All subjects with study vaccine administered	
Solicited local/general symptom	All subjects, with study vaccine administered, with at least one solicited symptom, either local or general, documented as either present or absent (i.e., symptom screen completed)	All study visits with study vaccine administered and with at least one solicited symptom, either local or general, documented as either present or absent (i.e., symptom screen completed)
Unsolicited symptom with onset within 30 days	All subjects, with study vaccine administered, that have safety data	
Unsolicited symptom (e.g., SAEs, AEs leading to withdrawal,..)	All subjects with study vaccine administered	

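### Surveillance for new SAEs and pIMDs is optional once a subject stops vaccine for a contraindication, and the SAP scores the unobserved time as event-free, giving a small downward bias

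*Protocol*

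**What the plan says.** **Follow-up after a vaccine stop.** For the absolute contraindications in protocol Section 6.5, "the subject must not receive additional doses of vaccine but may continue other study procedures at the discretion of the investigator". Section 8.2.1 gives the same latitude for pregnant or lactating subjects. For temporary contraindications, Section 6.5 allows later vaccination within the window, "or the subject may be withdrawn at the discretion of the investigator", without saying whether that means withdrawal from vaccine or from the study. Section 9.2.2 is also permissive: "A subject withdrawn from the study vaccines may not necessarily be withdrawn from the study as further study procedures or follow-up may be performed", if the protocol plans it.

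**What is mandatory.** Section 8.5.1.1 reviews open SAEs and pIMDs at later contacts. After discharge, Section 8.5.1.2 has the investigator follow subjects "With SAEs, pIMDs (serious or non-serious), or subjects withdrawn from the study as a result of an AE, until the event has resolved" or stabilised. Section 8.5.2 follows pregnancies to outcome.

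**The collection window.** Section 8.3.1 states: "The time period for collecting and recording SAEs will begin at the first receipt of study vaccine and will end at the last study visit". The pIMD window is the same. Section 8.3.2 adds that investigators need not actively look for events in former participants.

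**The analysis.** Any SAE and any pIMD from Day 1 to Day 541 are primary endpoints (Section 10.1). The Day 541 to 721 versions are secondary (Section 10.2). For SAE-type tables, SAP Section 11.2.5 divides by everyone who received study vaccine, and "Subjects who did not report the event or the concomitant medication will be considered as subjects without the event or the concomitant medication respectively". Section 9.2.1 keeps all data up to withdrawal or last contact.

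**The concern.** The primary objective is safety, and vaccine-induced autoimmune disease is the one theoretical vaccine risk named in protocol Section 1.3.1, with close monitoring of pIMDs as the mitigation. Under the text as written, a site may release a subject who has stopped vaccine, and no one is then obliged to ask about new SAEs or pIMDs. The analysis does not treat that time as missing: it enters the proportion as time without an event, over a fixed denominator. Neither document plans an exposure-time adjustment or a sensitivity analysis for it. Any resulting error in these proportions is downward, and it comes from subjects whose later course may differ from that of subjects who continue.

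**Working it through.** **Step 1: which endpoints can lose events.** The endpoints are subject-level occurrence (any SAE, any pIMD) and data before the stop are kept. A subject already in a numerator cannot be removed from it by later loss.

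| Reason for stop | Already counted | Still exposed to loss |
|---|---|---|
| Non-serious pIMD | Any pIMD to Day 541 | Any SAE to Day 541; later distinct events; both Day 541–721 endpoints |
| Malignancy, or anaphylaxis meeting the SAE definition (Section 8.1.2) | Any SAE to Day 541 | Any pIMD to Day 541; later distinct events; both Day 541–721 endpoints |
| Pregnancy, suspected immunodeficiency, injection judged unsafe | Nothing by virtue of the stop | Both primary and both secondary endpoints |

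**Step 2: the plan's own figure.** Section 10.4 gives a 95% probability of at least one event with N = 200 and incidence 1.50%. Poisson: 1 − exp(−200 × 0.015) = 1 − exp(−3.0) = 0.9502. Exact binomial: 0.9513. The figure reproduces.

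**Step 3: size to Day 541.** Inputs from the documents: N = 200, p = 1.5%, a 540-day window. Assumptions, because the documents give no rate of such stops:
- a share q = 1% or 2% of subjects stops without an event already counted in the endpoint and is not followed;
- they are lost from Day 61, the first visit at which a further dose is due, so 60/540 = 1/9 of the window is seen and 8/9 is not;
- the hazard is constant, and later risk is equal or threefold.

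Probability of an event before the stop: a = 1 − 0.985^(1/9) = 0.00168. 
Counted incidence: (1 − q) × 0.015 + q × a.
- q = 1%: 0.99 × 0.015 + 0.01 × 0.00168 = 1.487%
- q = 2%: 0.98 × 0.015 + 0.02 × 0.00168 = 1.473%

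True incidence at equal later risk is 1.500%. At threefold risk the unseen-period probability is b = 1 − (1 − 0.045)^(8/9) = 0.0401, and a stopper's overall probability is 1 − (1 − a)(1 − b) = 0.0417. The true incidence is then (1 − q) × 0.015 + q × 0.0417.

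| q | Later risk | True | Counted | Relative under-count | P(at least 1 event), full follow-up → as counted |
|---|---|---|---|---|---|
| 1% | equal | 1.500% | 1.487% | 0.9% | 0.950 → 0.949 |
| 2% | equal | 1.500% | 1.473% | 1.8% | 0.950 → 0.947 |
| 1% | threefold | 1.527% | 1.487% | 2.6% | 0.953 → 0.949 |
| 2% | threefold | 1.553% | 1.473% | 5.2% | 0.955 → 0.947 |

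The relative figures are the same at an incidence of 5% or 10%. In absolute terms, q = 2% loses about 200 × (1.500% − 1.473%) = 0.05 expected subjects with an event at equal risk, and 200 × (1.553% − 1.473%) = 0.16 at threefold risk.

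**Step 4: Day 541 to 721.** Here the whole window is unseen for a released subject, and an earlier event gives no credit. For rare events the relative under-count is q at equal risk (1% to 2%) and 3q/(1 − q + 3q) at threefold risk: 0.03/1.02 = 2.9% and 0.06/1.04 = 5.8%.

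**The case against.** The other side has real substance. Section 9.2.2 ties continued follow-up to what the protocol plans, and safety follow-up is planned: SAEs and pIMDs are recorded at every contact in Table 5, and Table 16 runs to Day 721. Known SAEs, pIMDs and pregnancies must be followed. Subjects are told to report symptoms they see as serious at once. Non-attenders get three calls and a certified letter. Related SAEs learned of after discharge must be notified. Withdrawals are tabulated by reason, so loss is partly visible. Entry criteria exclude autoimmune disease, suspected immunodeficiency and malignancy within 5 years, so few such stops are likely. Analyses are for estimation with no planned comparison, and the exact interval at 5% with N = 100 runs from 1.6% to 11.3% (Table 19), far wider than this bias.

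All of that limits the size. It does not close the gap. The contact attempts are for subjects who fail to return for scheduled follow-up, not for those a site has released. Section 8.3.2 removes the duty to seek events in former participants. A collection window does not by itself oblige anyone to make contact.

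Two stronger readings are tempting and fail:
- **That subjects stopped for anaphylaxis or a pIMD are counted as event-free.** Section 9.2.1 keeps data up to last contact. A subject stopped for a pIMD stays in the any-pIMD numerator, and anaphylaxis meeting the SAE definition stays in the any-SAE numerator. Only later, unobserved time is scored as event-free.
- **That 10% of subjects are affected.** The 10% in Section 10.4 is general drop-out for the third-dose immunogenicity evaluation, not a contraindication rate. Putting q = 10% into Step 3 gives under-counts of 8.9% and 22.7%, but nothing in the documents supports that input for this group.

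**Conclusion.** The point holds in a limited form. No sentence requires surveillance for new SAEs or pIMDs to Day 541 and Day 721 after a subject stops vaccine and is released, and the SAP treats the resulting silence as absence of an event. The bias is downward and restricted to the cells in the last column of the Step 1 table. With 1% to 2% of subjects affected, the Day 541 under-count is about 1% to 2% relative at equal later risk and up to about 5% at threefold risk; for Day 541 to 721 the upper figure is about 6%. These sizes rest on an assumed stop rate, early timing, constant hazard and an assumed risk ratio. The effect would not change the study's conclusions by itself. It is a cheap improvement worth making because it falls on primary safety endpoints with few expected events, and because the same counting rule applies to every early withdrawal.

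**What to change.** **Protocol.** In Sections 6.5 and 8.2.1, replace the discretionary wording, and in Section 9.2.2 the permissive wording, with a requirement: subjects who stop study vaccine for any reason are still contacted, by visit or telephone, for SAEs and pIMDs through Visit 9 and Visit 10 unless they withdraw consent. Blood sampling can stay optional. Section 5.6.18 already accepts a telephone contact as the concluding visit in special circumstances. Reconcile the withdrawal wording for temporary contraindications in Section 6.5 with the two definitions in Sections 9.2.1 and 9.2.2. No view is taken here on the contraindications or the dosing rule.

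**SAP.** In Section 11.2.5, report follow-up time by group and add an exposure-adjusted sensitivity analysis for SAEs and pIMDs, for Day 1 to 541 and Day 541 to 721. This also covers other early withdrawals and remains feasible if dosing is complete.

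**Cost.** A few sentences, a few extra contacts for subjects no longer receiving vaccine, and one extra table.
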